5.7 HRQL ASSESSMENT AT 15 MONTHS

HRQL will also be assessed 3 months after the exit DBPCFC. This can be done by email/online if preferred by the participant and their family.

5.8 OTHER ASSESSMENTS

5.8.1 ALLERGY SKIN PRICK TESTING

Skin prick testing (SPT) will be performed using ALK lancets (ALK-Abelló, Hørsholm, Denmark) on the volar side of the forearm of study participants, according to local standard operating procedures consistent with national guidelines.¹⁴

SPT will be measured at 15 minutes: the wheal will be traced around using pen and then an imprint taken with cellophane tape (e.g. sellotape); mean wheal diameter (average of longest length and its perpendicular width) will be measured.

SPT will be performed at the initial screening visit, 6 and 12 months after starting immunotherapy, using:

- Commercial extracts of whole CM and casein (ALK-Abelló, Hørsholm, Denmark), together with histamine positive and saline negative controls.
- Titrated SPT (end-point titration, EPT), to fresh* CM at the following concentrations:
 - neat, and
 - diluted (with sterile saline) at 1/10, 1/100, 1/1000, 1/10,000, 1/100,000

In addition, at *each* initial DBPCFC visit, SPT will be performed to fresh* CM and commercial CM extract (together with positive and negative control) prior to challenge. The wheal response will then be measured at approximately 30 minute intervals thereafter, until the wheal has reduced to 3mm or less, or the patient is discharged.

The time taken for the mean wheal size (elicited by SPT using neat milk or commercial extract) to reduce to 3mm (PT3) will be calculated using the following formula:

$$PT3 = T_1 + (3-W_1) \times \frac{T_2 - T_1}{W_2 - W_1}$$

where: T_1 = time when wheal diameter has reduced to < 3mm

W_1 = size of wheal at T_1 .

T_2 = time when wheal diameter has reduced to just above 3mm.

W_2 = size of wheal at T_2 .

*Fresh CM is not readily available in Spain. Therefore, SPT will be performed to freshly thawed cow's milk sourced from the UK market. Aliquots of fresh CM from the same batch of CM will be prepared in both centres and the frozen for use throughout the study for SPT. This has the added advantage of the same CM product being used throughout in both centres. We have previously demonstrated that a single freeze-thaw cycle of fresh CM does not affect SPT responses to CM.

¹⁴ http://www.bsaci.org/Guidelines/Skin_Prick_Testing.pdf

5.8.2 QUALITY OF LIFE ASSESSMENTS

The impact of OIT on participants' health-related quality of life (HRQL) will be assessed both from parents' and participants' perspective using abbreviated versions of disease-specific validated "food-allergy quality of life questionnaire" (FAQL-Q) in its parental,¹⁵ child¹⁶ and teenage¹⁷ forms at five time points during the study:

- i. baseline, at screening
- ii. baseline, after completion of the baseline DBPCFC
- iii. prior to the DBPCFC in between Phase 1 and Phase 2, at around 6 months
- iv. prior to the exit DBPCFC after Phase 2.
- v. 3 months after the exit DBPCFC (15 months visit).

These new abbreviated versions have been validated (data submitted for publication). We will also assess the impact of the child's food allergy on parent QoL using the FAQL-Parent Burden form (which has been validated in a UK population).¹⁸

The FAQL-questionnaires are based on a 7-point Likert scale and changes greater than 0.5 points over time have been defined as clinically significant.¹⁹ Previous studies have reported a positive effect on QoL following OIT to CM from the parents' perspective.²⁰ However, there are no controlled studies which have addressed the impact on QoL as perceived by the participants themselves. This is a significant knowledge gap, since there is a concern that while parents report an improved HRQL when their child undergoes immunotherapy the child themselves may experience a worsening of HRQL measures due to frequent side effects and need to alter their activities following immunotherapy doses.

In line with current expert opinion, and to ensure the ability to compare responses consistently during the 12 months of OIT, children who are age 12 at study commencement will be asked to complete the Teenage versions of the QoL assessments unless there are difficulties with comprehension which preclude this.

We will also assess HRQL using EQ-5D,²¹ a standardized instrument developed by the EuroQol Group as a measure of health-related quality of life that can be used in a wide range of health conditions and treatments, and is used by organisations such as the UK National Institute for Health and Care Excellence (NICE) to determine Quality-adjusted life year (QALYs). The EQ-5D consists of a descriptive system and the EQ Visual Analogue Scale, VAS. The descriptive system comprises five dimensions: mobility, self-care, usual activities, pain/discomfort and anxiety/depression. The EQ VAS records the patient's self-rated health on a vertical visual analogue scale. This can be used as a quantitative measure of health outcome that reflects the patient's own judgement. The scores on these five dimensions can be presented as a health profile or can be converted to a single summary index number (utility) reflecting preferability compared to other health profiles. EQ5D will be assessed at the same time points as FAQLQ.

¹⁵DunnGalvin A, Cullinane C, Daly DA, Flokstra-de Blok BM, Dubois AE, Hourihane JO. Longitudinal validity and responsiveness of the Food Allergy Quality of Life Questionnaire - Parent Form in children 0-12 years following positive and negative food challenges. *Clin Exp Allergy*. 2010;40:476-85.

¹⁶Flokstra-de Blok BM, DunnGalvin A, Vlieg-Boerstra BJ, et al. Development and validation of a self-administered Food Allergy Quality of Life Questionnaire for children. *Clin Exp Allergy*. 2009;39:127-37.

¹⁷Flokstra-de Blok B, DunnGalvin A, Vlieg-Boerstra BJ, et al. Development and validation of the self-administered Food Allergy Quality of Life Questionnaire for adolescents. *J Allergy Clin Immunol*. 2008;122:139-44, 144.e1-2.

¹⁸Knibb RC, Stalker C. Validation of the Food Allergy Quality of Life-Parental Burden Questionnaire in the UK. *Qual Life Res*. 2013;22:1841-9.

¹⁹Jaeschke R, Singer J, Guyatt GH. Measurement of health status. Ascertaining the minimal clinically important difference. *Control Clin Trials* 1989; 10:407-15.

²⁰Carraro S, Frigo AC, Perin M, et al. Impact of oral immunotherapy on quality of life in children with cow milk allergy: a pilot study. *Int J Immunopathol Pharmacol*. 2012;25:793-8.

²¹ <https://euroqol.org/eq-5d-instruments/>

Finally, we will include a brief self-efficacy assessment which evaluates participants (and their parents') ability to treat and manage their allergy, and how this changes during the trial. This questionnaire has been validated and used in a previous immunotherapy study in peanut allergy.

In subjects who are withdrawn from the study due to a significant allergic reaction, we will contact the family at 3 months later to repeat HRQL assessments. This will allow us to assess the impact of 'failing' immunotherapy on the young person and their family.

5.8.3 LABORATORY ASSESSMENTS

The development of tolerance in immunotherapy (whether to food or aeroallergens) is associated with several immunological changes, including decreases in CM-specific IgE levels with concomitant increases in IgG4 levels, reduced basophil and Th-2 cytokine responses to peanut stimulation and upregulation of IL-10-producing T-regulatory cells.²² Also specific IgA in saliva has been reported as a potential mechanism involved in effective SLIT to foods, at least to peanut.²³

It is therefore important for this study to include mechanistic assessments to better understand the ability of the different immunotherapy strategies tested to induce immune changes leading to desensitization. Additionally, various characteristics such as baseline allergen-specific IgE might be useful to predict the outcome of immunotherapy to foods. For instance, IgE binding to particular sets of CM peptides was found to be useful to predict the safety and efficacy of CM-OIT in a preliminary study.²⁴ The mechanistic work in this study will allow for markers of safe and successful desensitisation to be assessed, in order to improve the efficacy and safety of future immunotherapy protocols.

We will include a series of laboratory assessments in all subjects, allowing longitudinal comparisons amongst the different study groups as well as the evaluation of biomarkers that may identify successful desensitization to CM. These assessments will include:

- Changes in serum specific antibodies pre- and post-immunotherapy: Total IgE; specific IgE and IgG4 to CM and CM components (casein, alphalactalbumin and betalactoglobulin).
- CM-specific IgA in saliva using ELISA
- Identification of serum factors associated with the development of desensitization during CM immunotherapy.
- IgE and IgG₄ binding to CM epitopes, as assessed using a novel peptide microarray platform.
- Changes in T and B cell populations and their immune profile during CM immunotherapy including allergen-specific proliferation of T-cell subtypes (including T helper and regulatory T cells) and changes in immunoglobulin repertoire by CM-specific B-cells (London site only).

These assessments will be performed on blood samples taken at baseline, 6 and 12 months. Saliva samples will be collected using saliva oral swabs (Salivette, Sarstedt). Laboratory work will be initially performed at the National Heart & Lung Institute, Imperial College London, although some assays may be performed elsewhere in the UK and EU where lack of local expertise necessitates this. Consent will be requested for specimens to be stored for future use in new assays to measure immune responses or biomarkers.

²²Gorelik M, Narisety SD, Guerrero AL, et al. Suppression of the immunologic response to peanut during immunotherapy is often transient. *J Allergy Clin Immunol*. 2014; doi: 10.1016/j.jaci.2014.11.010.

²³Kulis M, Saba K, Kim EH, et al. Increased peanut-specific IgA levels in saliva correlate with food challenge outcomes after peanut sublingual immunotherapy. *J Allergy Clin Immunol*. 2012 Apr;129(4):1159-62.

²⁴Martínez-Botas J, Rodríguez-Álvarez M, Cerecedo I, et al. Identification of novel peptide biomarkers to predict safety and efficacy of cow's milk oral immunotherapy by peptide microarray. *Clin Exp Allergy*. 2015 Jun;45(6):1071-84.

5.8.3 ORAL AND FAECAL MICROBIOME ASSESSMENTS

As an exploratory analysis, we will collect both saliva and stool samples from participants at one of the baseline visits in order to assess oral and faecal microbiome in this unique population of children with persistent milk allergy. In conjunction with Nutricia Research / University of Utrecht (Netherlands), the following samples will be collected at the following time points from both participants but also, where consent is forthcoming, household siblings within 4 years of age older/younger than the participant with CM allergy taking part in the study.

	Oral microbiome	Faecal microbiome
Assessed at the following time points:		

Index case (study participant)Controls (household siblings)	
Baseline After Phase 1 (pre DBPCFC) After Phase 2 (pre DBPCFC)
 
Baseline only
	
Baseline only
 
Baseline only

Method of collection	
In study participants, the swab for salivary IgA will be collected first (see 5.8.3) and then the mouth rinsed with water.
 
Saliva for microbiome analyses will be collected using Oracol saliva collection system (Malvern Medical) as follows:
 
Rinse mouth with drinking water 10 minutes pre samplingPlace the sponge in the mouth between teeth and cheek for 2 minutes. Avoid changing position of the sponge, but if the sponge adheres to the cheek, rotate the sponge a quarter turn. If desirable, the sponge can be transferred to the other side of the mouth. After collection, store at -80°C until analysis. 
For siblings, the collection swab will be given to parents to collect saliva at home immediately prior to a study appointment.
	
Families will be given a sample collection pot(s) at screening and specimen bag and asked to bring the sample with them on one of the DBPCFC visits.

Table 8. Collection of samples for microbiome assessment

The use of household siblings as a control in the assessment of the oral and faecal microbiome is needed in order to control for environmental exposures which can significantly modify the microbiome and impair the assessment of changes in microbiota which might be due to atopic/allergic disease and how this might change during the course of oral immunotherapy.

Parents will be asked to collect these non-invasive samples from any household siblings under 16 years of age (within 4 years of age of the study participant with cow's milk allergy) so long as consent is provided by the parent/legal guardian and verbal assent by the sibling. Parents will be instructed not to force siblings to provide saliva/stool samples where verbal assent is not forthcoming.

Parents will also be asked to provide a minimum dataset of information relating to sibling controls:

- Age and gender
- Atopic status: eczema / asthma / food allergies / allergic rhinitis
- Brief dietary history of exposure of exposure to dairy products
- Any medical or surgical conditions affected the gastrointestinal system.

These data will be collected on a CRF and only identifiable through linkage to the index study participant.

5.9 STUDY COMPLETION

The study duration is approximately 15 months following enrolment. The study will be considered complete following enrolment of the last patient and completion of the study procedures in that patient.

At the end of the study, participants will be re-integrated into the routine clinical allergy service for ongoing care.

5.9.1 EARLY STUDY TERMINATION

An Independent Data Monitoring Committee (IDMC) will assess study safety on a regular basis. The IDMC has the authority to suspend the study, or request withdrawal of a particular participant at any stage if it concludes there are significant safety concerns affecting a single participant or the study as a whole.

Recruitment to the study and further CM challenges and updosing will be suspended pending review by the IDMC in the event of:

- any death
- a participant being admitted to the intensive care unit for a study-related adverse event
- a participant experiencing a life-threatening anaphylactic reaction to an immunotherapy dose.

The IDMC will consider the circumstances and make a recommendation as to whether to terminate the study or continue with or without a protocol amendment.

6. ADVERSE EVENT REPORTING

6.1 DEFINITIONS

An **adverse event** (AE) is any occurrence or worsening of an undesirable or unintended sign symptom, laboratory finding or disease that occurs during participation including occurrences that are not necessarily caused by or related to a study intervention. An adverse event will be followed until it resolves or until 30 days after a participant terminates from the study whichever comes first.

A **serious adverse event** (SAE) is defined as any adverse event that suggests a significant hazard. This includes but is not limited to any of the following:

1. Death: Any death that occurs during the study must be reported whether considered treatment related or not.
2. A life-threatening event: Any adverse therapy experience that in the view of the investigator places the participant at immediate risk of death from the reaction as it occurred. In line with guidance from the Food and Drug Administration (FDA) for Industry and Investigators²⁵, “it does not include an adverse event or suspected adverse reaction that, had it occurred in a more severe form, might have caused death.”
3. Inpatient hospitalization or prolongation of existing hospitalization.
4. Persistent or significant disability.
5. An event that requires intervention to prevent permanent impairment or damage. An important medical event that may not result in death, be life threatening or require hospitalization may be considered an SAE when based on appropriate medical judgment, it may jeopardize the participant and may require medical or surgical intervention to prevent one of the outcomes listed above.
6. Important AEs that are not immediately life-threatening or do not result in death or hospitalization but may jeopardise the subject or may require intervention to prevent one of the other outcomes listed in the definition above should also be considered serious.

The adverse event can be described as ‘**expected**’ if it caused symptoms and/or signs that could be reasonably described as a consequence of an allergic reaction to allergen exposure within the protocol. Symptoms of an allergic reaction are defined as any described within this protocol.

An adverse event is considered “**unexpected**” when its nature or severity is not consistent with the investigator’s protocol.

An adverse event is defined as “**related**” when it has resulted from the administration of any of the research procedures. Related adverse events are defined as “**adverse reactions**”.

²⁵ 2012 Food and Drug Administration (FDA) Guidance for Industry and Investigators, “Safety Reporting Requirements for INDs and bioavailability studies

All episodes of anaphylaxis occurring in response to a dose of SLIT/OIT will be treated as an AE "of interest" and reviewed by the Trial Management team.

The following criteria will constitute an SAE:

- Anaphylaxis occurring at in-hospital challenge *requiring* three or more doses of intramuscular adrenaline
- Anaphylaxis occurring in response to a dose of SLIT/OIT outside the hospital environment, requiring more than one dose of intramuscular adrenaline. **Such reactions will be classified as a SERIOUS ADVERSE REACTION.**
- Clinician-confirmed diagnosis of eosinophilic oesophagitis (with positive histology).

6.2 DOCUMENTATION OF ADVERSE EVENTS

All adverse events will be recorded on a specifically designated case report form (CRF) from the time the participant provides consent until the time the event resolves or until 30 days after the participant completes study treatment. Adverse events may be discovered through observing and questioning the participant or receiving an unsolicited complaint and questioning the participant in an objective manner. All adverse events will be recorded, regardless of their severity or relation to study medication or procedures.

All serious adverse events (SAEs) will be reported on a SAE report form in addition to CRFs. Safety data will be reviewed at least every four months by the Independent Data Monitoring Committee (IDMC). The IDMC has the authority to recommend withdrawal of a study participant or termination of the trial because of safety findings.

All SAEs should be reported to the Research Ethics Committee where, in the opinion of the Chief Investigator, the event was:

- 'related' i.e. resulted from the administration of any of the research procedures; and
- 'unexpected' i.e. an event that is not listed in the protocol as an expected occurrence

Reports of related and unexpected SAEs should be submitted within 15 days of the event using the NRES SAE form for non-IMP studies. The Chief Investigator must also notify the Sponsor of all SAEs. Any episode of anaphylaxis occurring outside DBPCFC challenge visits during the study, including those not classified as SAE, will be reported to the IDMC.

6.3 GRADING AND ATTRIBUTION OF ADVERSE EVENTS

Adverse events will be graded by the study site according to the criteria set forth in the NCI-CTCAE Version 3.0.²⁶ This document provides a common language to describe levels of severity to analyse and interpret data and to articulate the clinical significance of all adverse events:

- Grade 1 = mild adverse event.
- Grade 2 = moderate adverse event.
- Grade 3 = severe and undesirable adverse event.
- Grade 4 = life-threatening or disabling adverse event.
- Grade 5 = death.

All adverse events will be recorded and graded whether they are or are not related to disease progression or treatment. The NCI-CTCAE grades will be the primary source for scoring.

²⁶http://ctep.cancer.gov/protocolDevelopment/electronic_applications/docs/ctcaev3.pdf

Allergic reactions will be graded according to the CoFAR Grading System for Allergic Reactions, with additional modification to Grade 1 symptoms as shown in table 9. These can be used to inform as to the appropriate NTI-CTCAE grade.

Grade 1 – Transient	Grade 1- Mild	Grade 2 – Moderate	Grade 3 – Severe	Grade 4 – Life Threatening	Grade 5 - Death
Mild symptoms, <20mins. No impact on activity, no intervention needed. therapy required.	No or mild discomfort (< 48 hours).	Symptoms produce mild to moderate limitation in activity. Some assistance may be needed; no or minimal intervention/ therapy is required.	Marked limitation in activity. Some assistance usually required; hospitalisation is possible.	Extreme limitation in activity. Significant medical intervention is required; hospitalisation is probable.	Death
These symptoms may include pruritus, periorbital or facial angioedema, swelling or rash, mild abdominal discomfort, or other transient symptoms.		Hospitalization is possible but unlikely. These symptoms may include persistent hives, wheezing without dyspnea, abdominal discomfort / increased vomiting, or other symptoms	Symptoms may include bronchospasm with dyspnoea, severe abdominal pain, throat tightness with hoarseness, transient hypotension among others. Parenteral medication(s) are usually indicated.	Symptoms may include persistent hypotension and/or hypoxia with resultant decreased level of consciousness associated with collapse and/ or incontinence or other life-threatening symptoms.	

Table 9: CoFAR Specific Grading System for Allergic Reactions

The relation or attribution of an adverse event to study participation will be determined by the investigator and recorded on CRF and/or SAE reporting form. The assignment of the causality should be made by the investigator responsible for the care of the participant using the definitions in Table 10. If any doubt about the causality exists the investigator will discuss with the Chief Investigator. In the case of discrepant views on causality between the investigator and others, all parties will discuss the case.

Relationship	Description
Unrelated	There is no evidence of any causal relationship
Unlikely	There is little evidence to suggest there is a causal relationship (e.g. the event did not occur within a reasonable time after administration of the trial medication). There is another reasonable explanation for the event (e.g. the participant's clinical condition. other concomitant treatment).
Possible	There is some evidence to suggest a causal relationship (e.g. because the event occurs within a reasonable time after administration of the trial medication). However, the influence of other factors may have contributed to the event (e.g. the participant's clinical condition. other concomitant treatments).
Probable	There is evidence to suggest a causal relationship and the influence of other factors is unlikely.
Definitely	There is clear evidence to suggest a causal relationship and other possible contributing factors can be ruled out.
Not assessable	There is insufficient or incomplete evidence to make a clinical judgement of the causal relationship.

Table 10: Assignment of causality for adverse event

7. STATISTICS AND DATA ANALYSIS

7.1 SAMPLE SIZE ESTIMATION

The primary objective of the study is to assess the impact of a 6 month SLIT pretreatment phase on the safety of conventional OIT in children with persistent cow's milk allergy. The primary outcome is the proportion of participants experiencing adverse events classified as mild non-transient symptoms or more severe (see table 9) during CM-OIT (phase 2), in those who have received SLIT pretreatment (group S) compared to placebo (group C). As a secondary outcome, we will assess whether any effect of SLIT is dependent on the sublingual route, by including a third treatment group who have the same dosing regimen as the SLIT group but take the dose orally, omitting the sublingual phase (group O).

The expected natural resolution rate in CM allergic children beyond preschool age is less than 10% in a 6 months period.²⁷ Up to 70% of children undergoing conventional OIT for CM allergy experience mild, transient symptoms e.g. oropharyngeal itch [20.23.38]. A previous study in 9 peanut-allergic subjects showed a 75% relative reduction in mild non-transient symptoms (or symptoms of greater severity) during OIT as a result of the SLIT pretreatment.²⁸ Assuming 10% loss-to-follow-up, we calculate that a sample size of 66 participants (allocated 1:1:1 to the treatment groups) will detect a difference in the rate of children experiencing mild, non-transient symptoms from 70% in the OIT-alone group to 18% in the group undergoing SLIT pre-treatment prior to OIT (i.e. a 75% reduction), with 80% power at a significance level of $p<0.01666$ (Bonferroni correction) to allow for three pairwise comparisons (to ensure the overall risk of type I error is under 5%).

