7.2.1 ANALYSIS OF PRIMARY ENDPOINT

The primary analysis will compare the proportion of participants experiencing adverse events classified as mild non-transient symptoms or more severe (see table 9) during CM-OIT (phase 2), in those who have received SLIT pretreatment (group S) compared to placebo (group C) using a two-sided Fisher's exact test at a $p<0.05$ level of significance.

²⁷ Wood. J Allergy Clin Immunol. 2013 March ; 131(3): 805–812

²⁸ Narisety et al. J Allergy Clin Immunol. 2015 May;135(5):1275-82.e1-6.

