7.2.2 ANALYSIS OF SECONDARY ENDPOINTS

The following secondary analyses will be performed using two-sided testing for non-parametric data at a $p<0.05$ level of significance:

- The incidence of adverse events experienced (including rate of withdrawals, and anaphylaxis/adrenaline use during updosing) between groups S, O and C in phases 1 and 2. Statistical differences will be determined using Fisher's exact test for proportions or using non-parametric tests for graded reactions. Logistic regression will be used to assess the influence of age, gender, asthma status and prior history of anaphylaxis amongst other factors on the incidence of adverse events.
- Efficacy defined at DBPCFC as the proportion of study participants experiencing:
 - No symptoms (or only mild transient symptoms as per table 9) to 8 grams CM protein (approx. 250mls fresh milk) ("Complete desensitisation")
 - No symptoms (or only mild transient symptoms as per table 9) to at least 1.4 grams CM protein (approx. 45mls fresh milk) ("Partial desensitisation")
 - At least a 10-fold increase in eliciting dose (defined as the lowest dose which elicits objective symptoms or signs at challenge)....at 6 and 12 months in the different treatment groups, using a two-sided Fisher's exact test at a $p<0.05$ level of significance.
- This will include a comparison of the efficacy of SLIT compared to the same dose administered orally without a sublingual phase (to address hypothesis 2), and its effect on the subsequent safety of OIT.
 - Immunological outcomes (titrated skin prick test, serum IgE) at baseline, 6 and 12 months.
 - Change in health-related quality of life (HRQL) measures at 6, 12 and 15 months, as assessed by validated questionnaires (FAQLQ, FAIM, EQ-5D) in study participants and their parents.
- Change in health-related quality of life (HRQL) measures at 6, 12 and 15 months, as assessed by validated questionnaires (FAQLQ, FAIM, EQ-5D) in study participants and their parents.
- Immunological outcomes (titrated skin prick test, serum IgE) at baseline, 6 and 12 months.
- The trend in CM-peptide binding over time as well as the potential influence of baseline peptide binding on the outcome of CM-IT will be assessed using a bioinformatics approach as in previous studies.²⁹

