Secondary analyses will include a comparison of the safety/efficacy of SLIT compared to the same dose administered orally without a sublingual phase (to address hypothesis 2), and its effect on the subsequent safety/efficacy of OIT.

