7.2.3 INTERIM ANALYSIS

There will be no formal interim analysis, however the IDMC will review safety data at least every 6 months.

²⁹ Martínez-Botas J, et al. Clin Exp Allergy. 2015 Jun;45(6):1071-84.

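### The 0.01666 Bonferroni level that Section 7.1 uses to size the trial and to claim overall type I error under 5% is not carried into the tests in Sections 7.2.1 and 7.2.2, which use 0.05

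*Combined protocol and SAP*

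**What the plan says.** Section 7.1 gives the sample size: "Assuming 10% loss-to-follow-up, we calculate that a sample size of 66 participants", allocated 1:1:1, to detect a fall from 70% to 18% in the proportion of children with mild non-transient or worse events in phase 2, "with 80% power at a significance level of $p<0.01666$ (Bonferroni correction) to allow for three pairwise comparisons". It states the purpose of the correction: "to ensure the overall risk of type I error is under 5" per cent.

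The analysis sections use another level. Section 7.2.1 compares S with C by a two-sided Fisher's "exact test at a $p<0.05$ level of significance". Section 7.2.2 specifies "two-sided testing for non-parametric data at a $p<0.05$ level of significance" for the secondary analyses, among them adverse events "between groups S, O and C in phases 1 and 2". It also adds: "Secondary analyses will include a comparison of the safety/efficacy of SLIT compared to the same dose administered orally without a sublingual phase".

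Sections 3.1.1, 7.1 and 7.2.1 all name S vs C as the primary comparison. Section 3.1.2 makes S vs low-dose oral pretreatment (O) on the same outcome secondary. No section names O vs C on that outcome; the wording in 7.1 and 7.2.2 only implies it. Section 7.2.3 says "There will be no formal interim analysis", so no interim look accounts for the stricter level.

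**The concern.** A Bonferroni correction controls error only if the tests use it. Section 7.1 promises an overall type I error across three comparisons, but the written decision rules apply 0.05 to each test, with no hierarchy or other adjustment. The 80% power also belongs to a test at 0.01666, which 7.2.1 does not perform.

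The practical risk is a dispute over the primary result. A p-value between 0.01666 and 0.05 is significant under 7.2.1 but misses the level used to size the trial. If this is settled after unblinding, the rule will appear to have been chosen to suit the result.

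**Working it through.** **Inputs.** Section 7.1: rates 70% (C) and 18% (S), 66 randomised 1:1:1 (22 per arm), 10% loss, 80% power, level 0.01666. Sections 7.2.1 and 7.2.2: level 0.05, with two-sided Fisher's exact test for proportions. Evaluable number: 66 × 0.9 = 59.4, or 19.8 per arm, so 19-20. Section 7.2 specifies intention-to-treat, so 22 per arm is also shown.

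**The plan's own level.** 0.05/3 = 0.016667, given as 0.01666. Three tests at that level sum to 3 × 0.01666 = 0.04998, so the claim in 7.1 would hold if the level were used. At 0.05 the same bound is 3 × 0.05 = 0.15, and the guarantee no longer follows. The sample-size formula is not stated. Of the normal-approximation variants tried at 0.01666 for 70% vs 18%, only the one-sided, continuity-corrected one gives 66 (19 per arm, 22 after loss). The two-sided versions give 60 without continuity correction and 75 with it.

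**Actual error.** The 0.15 bound overstates the problem, because Fisher's test is conservative at this size. The exact probability of at least one rejection sums the product of the binomial probabilities over all outcome tables in which any of the pairwise tests rejects. With all arms sharing one event rate between 30% and 70% (rates 30, 40, 50, 60 and 70% enumerated):

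| Tests performed | 20 per arm | 22 per arm |
|---|---|---|
| S vs C only, at 0.05 | 2.0-2.5% | 2.2-2.4% |
| S vs C and S vs O, at 0.05 | 3.8-4.6% | 4.1-4.4% |
| All three pairs, at 0.05 | 5.1-6.3% | 5.7-6.1% |
| All three pairs, at 0.01666 | 1.7-1.8% | 2.0-2.6% |

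At a common rate of 10% and 20 per arm, three tests at 0.05 give 3.2%. If only one pair is truly null there is no excess: with O = C = 70% and S = 18%, the error is 2.5% (20 per arm) or 2.4% (22); with S = O = 18% and C = 70%, it is 2.2% or 2.4%.

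**Power.** The sum of Binomial(x; n_S, 0.18) × Binomial(y; n_C, 0.70) over tables with Fisher p below alpha:

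| n_S / n_C | alpha 0.01666 | alpha 0.05 |
|---|---|---|
| 19/19 | 72.2% | 88.7% |
| 19/20 | 79.5% | 90.0% |
| 20/19 | 80.6% | 90.4% |
| 20/20 | 77.2% | 88.4% |
| 21/21 | 81.7% | 89.7% |
| 22/22 | 85.4% | 91.9% |

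**Results between the two levels.** Under 70% vs 18%, the probability that 0.01666 ≤ p < 0.05 is the difference between the columns: 11.2% at 20 per arm and 6.5% at 22. Examples: 6/20 vs 14/20 gives p = 0.026; 7/22 vs 15/22 gives p = 0.034.

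**The case against.** The strongest reply is that nothing is wrong with the primary test. S vs C is the sole primary comparison, 7.2.1 gives a complete rule for it, its size is well under 5%, and sizing at a stricter level than the test uses errs on the safe side. The two pairs explicitly named on the primary outcome, S vs C and S vs O, together stay below 5% even at 0.05. An excess appears only if O vs C is added and all arms share one rate, and it is then about one point.

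All of that stands, and it limits the size of the problem. It does not reconcile the text. Section 7.1 does not present 0.01666 as a safety margin; it claims overall error control across three comparisons, which only the analysis can provide. In a three-arm trial, three pairwise comparisons include O vs C. If S vs C at 0.05 is the intended rule, the Bonferroni sentence and the 80% power are wrong; if the Bonferroni sentence is intended, 7.2.1 is wrong.

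It is also fair that the documents do not show which level was meant, so the choice of remedy is a judgement. The shortfall below 80% power at 0.01666 is partly an effect of discreteness: power moves between 72% and 81% as the arms vary between 19 and 20, and reaches 85% if all 22 are analysed.

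**Conclusion.** The concern holds and should be fixed, though its numerical effect is small. The error-control statement in 7.1 is not delivered by the tests in 7.2, and the stated 80% power does not describe the 7.2.1 test, whose power is about 88-90% with 19-20 evaluable per arm and 92% with 22. The primary test itself is not inflated. The excess over 5% is at most about 1.3 points in the cases enumerated (6.3% at 20 per arm, rates 30-70%) and requires both that O vs C is tested and that all three arms have the same rate.

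The larger practical exposure is the 6.5-11.2% chance, under the planned effect with 22 or 20 per arm, of a primary p-value on which the two sections disagree. These figures assume Fisher's test on independent binomial counts and, for the power figures and that chance, the plan's rates of 70% and 18%.

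**What to change.** State one alpha rule, identically in 7.1 and 7.2, before any unblinded outcome data are seen.

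- **Preferred.** Keep S vs C as the single primary comparison at two-sided 0.05. Remove the Bonferroni and overall-error wording from 7.1. Restate Fisher power as about 88-90% with 19-20 evaluable per arm (92% with all 22). Label S vs O and O vs C as secondary and unadjusted, or pre-specify an adjustment. Cost: wording only, no extra participants.
- **Alternative.** Write 0.01666 into 7.2.1 and into the pairwise safety comparisons in 7.2.2. Restate Fisher power as 77% at 20/20 evaluable (72% at 19/19, 79-81% with one arm at 19 and the other at 20, 85% at 22/22). Cost: wording only if that power is accepted. Otherwise the smallest equal arm size giving at least 80% is 21 evaluable; 21/0.9 = 23.3, so 24 per arm or 72 randomised if rounded up within arms. Rounding over the whole trial, 69 is arguable (69 × 0.9 = 62.1 evaluable).

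Either way, say whether O vs C on the primary outcome is one of the three comparisons.
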